Study Design	
This is a randomized, open-label, multi-center phase II clinical study. Eligible subjects after screening will be randomized into the following three groups in a 1:1:1 ratio, with 4 weeks as 1 treatment cycle:
 
A: SHR-1210 200 mg, IV, Q2W + apatinib 375 mg, PO, QD
 
B: SHR-1210 200 mg, IV, Q2W + apatinib 375 mg, PO, QD (5 days on, 2 days off)
 
C: SHR-1210 200 mg, IV, Q2W + apatinib 375 mg, PO, QD (7 days on, 7 days off)
 
The study consists of two stages. In Stage I, subjects will be randomized into 3 different dose groups, with 6 subjects in each group. It is planned that after the last subject in Stage I completes Cycle 1 treatment (28 days), the leading center's principal investigator and the sponsor will jointly perform a safety assessment of subjects enrolled in Stage I, decide the treatment group of Stage II, and choose one group of method of administration and a tolerated dose of apatinib for Stage II treatment.
 
A total of 39 subjects will be enrolled in Stage II. The primary analysis will be performed when the last subject has been treated for 180 days.
 
For any treatment group entering Stage II, if the safety is acceptable and the efficacy meets the corresponding statistical criteria, it indicates potential needs of further development.

Study Drugs and Method of Administration	
A: SHR-1210 200 mg, IV, Q2W + apatinib 375 mg, PO, QD
 
B: SHR-1210 200 mg, IV, Q2W + apatinib 375 mg, PO, QD (5 days on, 2 days off)
 
C: SHR-1210 200 mg, IV, Q2W + apatinib 375 mg, PO, QD (7 days on, 7 days off)
 
Note: PO: per os; QD: quaque die; IV: intravenous infusion; Q2W: once every 2 weeks; 5 Days on, 2 Days off: administration for 5 days and interrupt for 2 days; 7 Days on, 7 Days off: administration for 7 days and interrupt for 7 days

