Day	-28 to -1	-7 to 1	-3 to 1	1	15 (± 3 days)	1 (± 3 days)	15 (± 3 days)	± 3 days	90 days (± 7 days)
Peripheral Blood ²⁴	X					X		X	

Note:

1. Except for tumor imaging and tumor biopsy within the prescribed time limit before the first dose, the ICF should be signed before any operation specified in the protocol.
2. The medications include treatment for initial diagnosis, including chemotherapy, radiotherapy, and surgical treatment. The time of the last anti-tumor treatment must be recorded.
3. Vital signs include body temperature, pulse, respiratory rate, and blood pressure. Measurements will be conducted during the screening period, before each SHR-1210 administration, at the end of the treatment, and at safety follow-ups. Blood pressure monitoring: cigarettes and caffeine are prohibited within 30 min before each blood pressure measurement, and subjects shall rest for at least 10 min. The blood pressure will be measured at sitting position with elbow on the same level as heart. All measurements should be taken on the same side. During the screening period and before each scheduled SHR-1210 infusion, the investigator will measure the blood pressure of the subject. During the study, the subject will monitor the blood pressure and record on the diary card. Blood pressure shall be measured at least 3 times per week in the first 2 cycles. For subjects with abnormal blood pressure, the blood pressure shall be measured daily; if normal, the blood pressure shall be measured twice per week after Cycle 2.
4. Height will be measured only during the screening period. Weight will be measured during the screening period, before each SHR-1210 administration, at the end of the treatment, and at safety follow-ups.
5. Physical examinations will be conducted during the screening period, before each SHR-1210 administration, at the end of the treatment, and at safety follow-ups.
6. ECOG PS scoring will be conducted during the screening period, before each SHR-1210 administration, at the end of the treatment, and at safety follow-ups.
7. 12-lead ECG examination time: during the screening period, after each SHR-1210 infusion, at the end of treatment, and during safety follow-up. The examination results during screening may be used for the ECG examination at C1D1 visit. Refer to Section 8.2.3 of the protocol for details.

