8. Hematology includes: red blood cell count (RBC), hemoglobin (HGB), hematocrit value (HCT), white blood cell count (WBC), platelet (PLT), and white blood cell differential [lymphocyte count (LYM), absolute neutrophil count (ANC), monocyte count (MONO), eosinophil count (EOS), and basophil count (BASO)]. Clinical chemistry includes: liver function [serum total bilirubin (TBIL), alanine aminotransferase (ALT), aspartate transferase (AST), gamma-glutamyltransferase (γ -GT), alkaline phosphatase (ALP), albumin (ALB), total protein (TP), and lactic dehydrogenase (LDH)]; renal function [blood urea nitrogen (BUN) and creatinine (Cr)]; blood electrolytes (Na, K, Cl, Mg, Ca, and P); lipase, amylase, and fasting blood glucose (FBG). Urinalysis includes: pH, urine albumin (UALB), urine protein (UPRO), urine red blood cell (URBC), and urine glucose (UGLU). The subject may be enrolled only if urinalysis shows negative urine protein at screening. Routine stool test: occult blood; re-examination is needed for fecal occult blood+; if fecal occult blood is confirmed, then a gastroenterological endoscopy will be performed. Hematology, clinical chemistry, urinalysis, and routine stool will be performed during the screening period (within 7 days before the first dose of the study drug), before each SHR-1210 administration, at the end of the treatment, and at safety follow-ups. Tests will be performed at each study center.
9. Coagulation function tests include: thrombin time (TT), prothrombin time (PT), activated partial thromboplastin time (APTT), and international normalized ratio (INR). Tests will be performed within 7 days prior to the first dose, before the administration of SHR-1210 on day 1 of each cycle, at the end of the treatment, and at safety follow-ups. Tests will be performed at each study center.
10. Women of childbearing potential will undergo a serum pregnancy test within 3 days prior to the first dose and at the end of the treatment. Tests will be performed at each study center.
11. Thyroid function tests include: thiiodothonine (T3), thyroxine (T4), free thiiodothonine (FT3), free thyroxine (FT4), and thyroid stimulating hormone (TSH). Tests will be performed during the screening period, before the administration of SHR-1210 on day 1 of each cycle, at the end of the treatment, and at safety follow-ups; the results from the screening period may be used for the thyroid function tests at the C1D1 visit. Tests will be performed at each study center.

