6 STUDY DRUGS

6.1 Treatment Regimen

6.1.1 Administration regimen

Study drugs refer to SHR-1210 and apatinib, and other drugs during the study are non-study drugs. Refer to [Table 5](#) for the treatment regimen. For the ease of liquid preparation, the protocol allows a deviation of $\pm 5\%$ between the actual dosage and the theoretical dosage each time.

The study drugs will be administered until PD (refer to Section 6.1.2 for continued medication beyond progression), intolerable toxicity, withdrawal of ICF, other reasons that require treatment discontinuation (whichever occurs first)

Table 5. Treatment regimen

Phase	Drug	Dose	Route of Administration	Administration Cycle
II	SHR-1210	200 mg	IV	Q2W
	Apatinib, combined	375 mg	PO	QD
	SHR-1210	200 mg	IV	Q2W
	Apatinib, combined	375 mg	PO	QD (5 days on, 2 days off)
	SHR-1210	200 mg	IV	Q2W
	Apatinib, combined	375 mg	PO	QD (7 days on, 7 days off)

Note:

1. On the day of SHR-1210 infusion, apatinib shall be administered 30 min after the end of SHR-1210 infusion.
2. SHR-1210 is administered through intravenous drip infusion at 200 mg once every 2 weeks with 4 weeks as 1 treatment cycle.
3. Apatinib is administered orally once daily after meal with 4 weeks as 1 treatment cycle. Subjects are randomized into the three groups in a 1:1:1 ratio. Drugs should be administered at a fixed time every day as much as possible.
4. PO: per os; QD: quaque die; IV: intravenous infusion; Q2W: once every 2 weeks; 5 Days on, 2 Days off: administration for 5 days and interrupt for 2 days; 7 Days on, 7 Days off: administration for 7 days and interrupt for 7 days

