5.5.3 Vital signs

Vital sign measurements at each scheduled visit point (including baseline) will be summarized and listed using descriptive statistics. Changes in vital signs from baseline at each visit point after baseline will be summarized and listed using descriptive statistics.

Baseline is defined as the last measurement before the first dose.

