6 INTERIM ANALYSIS

It is planned that after the 18th subject in Stage I completes Cycle 1 treatment (28 days), a safety analysis will be conducted. The leading center's principal investigator and the sponsor will jointly perform a safety assessment of subjects enrolled in Stage I and decide the treatment groups of Stage II.

This analysis only provides a listing of subjects' AEs and laboratory evaluations and does not involve the analysis of the efficacy endpoints.

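### In Stage I the scheduled laboratory and urine tests fall 1, 3 and 8 days after the last apatinib dose in groups A, B and C, so they are not like for like when the schedule is chosen

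*Protocol*

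**What the plan says.** The Protocol synopsis defines three groups with the same SHR-1210 regimen and the same apatinib dose; only the apatinib days differ. Group A is daily: "A: SHR-1210 200 mg, IV, Q2W + apatinib 375 mg, PO, QD". Group B follows a weekly pattern: "5 Days on, 2 Days off: administration for 5 days and interrupt for 2 days". Group C alternates seven days on and seven off.

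Protocol 6.1.1 fixes the infusion calendar: "SHR-1210 is administered through intravenous drip infusion at 200 mg once every 2 weeks with 4 weeks as 1 treatment cycle". It also ties apatinib to it: "On the day of SHR-1210 infusion, apatinib shall be administered 30 min after the end of SHR-1210 infusion".

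Table 1, note 8 puts hematology, chemistry, urinalysis and stool tests in the 7 days before first dose and then "before each SHR-1210 administration, at the end of the treatment, and at safety follow-ups. Tests will be performed at each study center". Neither Table 1 nor Table 12 marks this panel at Cycle 1 Day 1. The first on-treatment mark is Cycle 1 Day 15 (±3 days), followed by Days 1 and 15 of later cycles.

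Clinic vital signs follow the infusion days too, but subjects also keep a blood-pressure diary (Table 1, note 3): "Blood pressure shall be measured at least 3 times per week in the first 2 cycles".

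Stage I randomizes 6 subjects to each group, and one schedule is chosen once the last of them completes 28 days (Protocol 4). On the data for that choice, SAP 6 says: "This analysis only provides a listing of subjects' AEs and laboratory evaluations and does not involve the analysis of the efficacy endpoints". SAP 5.5.3 says: "Vital sign measurements at each scheduled visit point (including baseline) will be summarized and listed using descriptive statistics". Neither section mentions the diary readings.

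**The concern.** Stage I exists to choose among schedules that differ only in when apatinib is taken. Laboratory sampling is locked to a 14-day infusion calendar, and 14 days is a whole number of both the 7-day pattern in B and the 14-day pattern in C. Every nominal test therefore catches each group at one fixed point of its pattern. In C that point is the end of the off-week.

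A laboratory abnormality that appears in an on-week and resolves in the off-week could be seen in A and missed in C. Symptoms would still be reported, but a silent fall in blood counts, rise in transaminases or proteinuria comes to light only through a test. For proteinuria, Protocol 6.4.2 starts from the scheduled urinalysis. With 6 subjects per group, one missed case moves an observed rate by 1/6, about 17 percentage points. The shift favors the schedule with the longest break.

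**Working it through.** **Inputs.** Infusions on nominal Days 1, 15, 29 and so on (Protocol 6.1.1). Apatinib patterns from the synopsis. Tests taken before the infusion (Table 1, note 8), and so before that day's apatinib. On-block assumed to open on Day 1.

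**Step 1: dosing days.** For day d, A doses every day; B doses if (d − 1) mod 7 < 5; C doses if (d − 1) mod 14 < 7. Over Days 1 to 28 this gives 28, 20 and 14 days, which reproduces the table in SAP 5.3.2.

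**Step 2: gap at the test.** Gap = test day minus last earlier dosing day.

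| | A | B | C |
|---|---|---|---|
| Last dose before Day 15 | Day 14 | Day 12 | Day 7 |
| Gap at Day 15 | 1 | 3 | 8 |
| Last dose before Day 29 | Day 28 | Day 26 | Day 21 |
| Gap at Day 29 | 1 | 3 | 8 |
| Doses in the preceding 7 days, either test | 7 | 5 | 0 |

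Days 43 and 57 give the same figures.

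**Step 3: panels in the Stage I window.** At nominal timing, Day 15 is the only scheduled on-treatment panel within Days 1 to 28; the next is Day 29.

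**Step 4: the ±3-day window.** If the apatinib calendar stays fixed while the visit moves:

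| Visit day | 12 | 13 | 14 | 15 | 16 | 17 | 18 |
|---|---|---|---|---|---|---|---|
| Gap, A | 1 | 1 | 1 | 1 | 1 | 1 | 1 |
| Gap, B | 1 | 1 | 2 | 3 | 1 | 1 | 1 |
| Gap, C | 5 | 6 | 7 | 8 | 1 | 1 | 1 |
| Doses in C, preceding 7 days | 3 | 2 | 1 | 0 | 1 | 2 | 3 |

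The preceding 7 days hold 7 doses in A and 5 in B throughout. If instead C's on-block waits for the infusion, a Day 18 visit is 18 − 7 = 11 days after its last dose. The documents do not say which applies.

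**Step 5: the starting phase.** An off-first calendar would give gaps of 1 day in B and C at Day 15. It would also put infusion days in C's off-week, which fits poorly with the instruction to take apatinib after the infusion. On-first is the natural reading, but it is inferred.

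**Step 6: home blood pressure.** Three readings a week over four weeks is at least 12 in Cycle 1. C's on-weeks are weeks 1 and 3, so at least 6 of those readings fall in on-weeks.

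**The case against.** The other side is strong on scope. Adverse events are recorded continuously from consent (Table 1, note 18), so on-week symptoms in C count. Diary blood pressure covers on-weeks, and raised readings can enter as adverse events. Unscheduled results are also used (SAP 5.5), and shift tables take the worst post-baseline result (SAP 5.5.2). Drug use is listed in detail (SAP 5.3), so dose timing could be worked out. Recovery during a planned break is partly a real property of an intermittent schedule.

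Most of this stands, and it rules out several stronger readings:

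- A reader might infer that every scheduled test, or the whole Stage I comparison, sees C off apatinib. Home blood pressure, adverse events, and end-of-treatment and follow-up tests are not tied to infusion days.
- A reader might extend the 8-day gap to ECG. ECG follows the infusion (Table 1, note 7), and its order relative to that day's apatinib is not stated. ECG and vital-sign values are also not in the listing that SAP 6 describes.
- A reader might carry the bias into the primary safety endpoint in Stage II. One schedule goes forward, so no schedules are compared there. The laboratory component counts only Grade 3 or higher abnormalities that prompt intervention or hospitalization or last 7 days or more.
- A reader might put a size on the bias from an assumed decay. Half-lives of 2 and 7 days give a C-to-A ratio of 0.5^(7/2) = 0.09 and 0.5^(7/7) = 0.50. That spread comes from the assumption, as does the premise of equal on-drug effect and one decay pattern for every parameter.

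The objections do not remove the narrower point. No scheduled test prompts an on-week sample in C at nominal timing. Even a Day 16 to 18 visit on a fixed calendar follows only 1 to 3 doses after a week off.

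**Conclusion.** The point holds for scheduled hematology, chemistry and urinalysis in Stage I. At nominal Days 15 and 29 they are taken 1, 3 and 8 days after the last apatinib dose in A, B and C. For clinically silent laboratory toxicity, this can make C, and to a lesser degree B, look better tolerated than A.

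The conclusion assumes an on-block that opens on Day 1 and visits at nominal timing. The window changes C's gap, but C still has fewer recent doses than A or B. Direction and timing follow from the documents; the size of the effect does not. It is an interpretive weakness in one part of a small descriptive comparison, worth correcting because the correction is cheap.

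**What to change.** Amend SAP 6 and 5.5.3 as follows:

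1. Add the diary blood pressures to the Stage I listing and to the vital-sign section, split into days with and without a recorded apatinib dose.
2. Beside each laboratory and urine result, show days since last apatinib dose: test date minus the latest dosing date before the test, taken from the administration records that SAP 5.3.2 already uses.
3. State that scheduled laboratory results are not read across the three groups as like for like.

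This is SAP wording applied to information already recorded. The cost is a little more data entry and listing work for the diary readings. An extra on-week laboratory panel in Stage I would be optional; it would add a visit and require a protocol amendment, and is not part of this fix.

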2 BACKGROUND AND SCIENTIFIC RATIONALE

2.1 Disease Background

Lung cancer is the most common malignant tumor in China. According to data released by the National Center for Cancer Registry in 2016, the incidence of lung cancer ranked first in males and second only to breast cancer in females [1]. The main types include non-small cell lung cancer (NSCLC) and small cell lung cancer (SCLC).

2.1.1 Non-small cell lung cancer

NSCLC accounts for approximately 85% of lung cancers^[2,3]. NSCLC is classified by histology as adenocarcinoma, squamous carcinoma, large cell carcinoma, neuroendocrine tumor, sarcomatoid carcinoma, and poorly differentiated carcinoma. Among these subtypes, adenocarcinoma accounts for more than 50% and squamous cell carcinoma accounts for 25%^[4]. The 5-year survival rate of NSCLC is 2-4%, depending on the lesion site^[5]. Factors for poor prognosis include advanced stage at initial diagnosis, poor PS score, and history of surreptitious weight loss. Half of NSCLC patients have distant metastases when initially diagnosed.

Adenocarcinoma and squamous cell carcinoma have different characteristics. First, squamous cell carcinoma is commonly the central type and mostly in the bronchial epithelium, whereas non-squamous carcinoma is commonly the peripheral type and mostly in the lung parenchyma. Evaluation of the histological type of NSCLC further shows the difference between squamous cell carcinoma (keratinization, intracellular bridges, and central necrosis) and adenocarcinoma (glandular structure). Immunohistochemical labeling further supports the diagnosis of NSCLC when the tumor specimens are limited in quantity or the degree of differentiation is low. TTF-1 is expressed highly in adenocarcinoma but rarely in squamous cell carcinoma. On the contrary, p63, CK5/6, and 34BE12 are highly expressed in squamous cell carcinoma but rarely in adenocarcinoma^[6].

The driver genes of NSCLC include EGFR, ALK, and KRAS. These driver genes have different mutation rates in adenocarcinoma and squamous cell carcinoma. For example, 10-40% of adenocarcinoma patients are EGFRm+. Approximately 7% of adenocarcinoma patients are ALK fusion gene positive. And approximately 30% of adenocarcinoma patients are KRASm+. But these gene mutations are rare in patients with squamous cell carcinoma^[4,6,7].

See [Table 2](#) for the treatment of different types of NSCLC recommended by the FDA and EMA. No immunotherapy drug is available in China for the treatment of advanced NSCLC (Stage IV) with negative driver genes according to the guidelines of the Chinese Society of Clinical Oncology (CSCO) issued in 2017. For the second-line treatment of non-squamous cell carcinoma, mono-chemotherapy with docetaxel or pemetrexed is recommended for patients with a PS score of 0-1. The best supportive treatment is recommended for patients with a PS score of 3-4, who are encouraged to participate in clinical studies. Mono-chemotherapy with docetaxel is recommended as second-line treatment of squamous cell carcinoma. Patients who are not suitable for cytotoxic chemotherapy may choose afatinib, vinorelbine, or gemcitabine. Few second-line treatment options are available for NSCLC, and new treatment methods are urgently needed. Most immunotherapy, anti-VEGFI therapy, immunotherapy-based combination therapy, or anti-VI(R)-based combination therapy are still under clinical studies.

Table 2. Individualized treatment of NSCLC

Histology	Molecular Pathology	PD-L1 Expression*	First line	Maintenance	Second Line
Squamous cell cancer	NA	< 50%	Platinum-based chemotherapy ± necitumumab (EMA)	Necitumumab	Immunotherapy
					Chemotherapy
	NA	≥ 50%	Pembrolizumab	Pembrolizumab	Docetaxel + ramucirumab
					Afatinib
EGFRm+	NA	NA	Erlotinib + bevacizumab	Erlotinib + bevacizumab	Osimertinib
			Erlotinib	Erlotinib	Platinum-based chemotherapy
			Afatinib	Afatinib	
			Gefitinib	Gefitinib	
Non-squamous cell cancer	ALK+	NA	Crizotinib (also applicable to ROS1+)	Crizotinib (also applicable to ROS1+)	Ceritinib
					Alectinib
	Wild-type	< 50%	Ceritinib (FDA and EMA)	Ceritinib (FDA and EMA)	(failure of first-line treatment with crizotinib)
					Platinum-based chemotherapy
	Wild-type	< 50%	Platinum-based chemotherapy (± bevacizumab)	Pemetrexed (continued or transferred to maintenance treatment)	Immunotherapy
				Bevacizumab (continued maintenance treatment)	Chemotherapy
				Docetaxel + ramucirumab	Docetaxel + nintedanib (adenocarcinoma, EMA)
					Erlotinib (EMA)
	Wild-type	≥ 50%	Pembrolizumab	Pembrolizumab	Platinum-based

Note: This table is from Reference 8.* Dako 22C3 kit is used for the detection of PD-L1.

2.1.2 Small cell lung cancer

SCLC accounts for 10-15% of new lung cancers. It is a highly aggressive neuroendocrine tumor. It is significantly different from NSCLC clinically and pathologically, characterized by rapid growth, proneness to drug resistance, and early metastasis. Almost all patients with SCLC have a history of heavy tobacco use^[9,10]. Traditionally, SCLC is classified into limited-stage disease (LD-SCLC, where tumor tissue surrounds a radiotherapy field) and extensive-stage disease (ED-SCLC, where tumor tissue exceeds the boundary of a radiotherapy field)^[11]. Most patients have ED-SCLC when first diagnosed. Platinum (cisplatin or carboplatin) combined with etoposide for 4-6 cycles is still the first-line standard treatment for LD-SCLC and ED-SCLC. The combination of platinum, etoposide, and thoracic radiotherapy can reach an ORR of 70-90% in LD-SCLC. The combination of platinum and etoposide can reach an ORR of 60-70% in ED-SCLC. The mOS is 14-20 months and 9-11 months, respectively. After proper treatment, the 2-year survival rate is 40% and < 5%, respectively^[12]. Concomitant thoracic radiotherapy can increase the local control rate by 25% in LD-SCLC ^[13,14]. The combination of radiotherapy and chemotherapy are recommended for LD-SCLC patients with negative cytological results or uncertain pleural effusion without pericardial effusion^[15,16].

After the first-line treatment with the combination of platinum and etoposide, approximately 80% of LD-SCLC patients and almost all ED-SCLC patients develop progressive disease^[17]. Subjects whose last dose of first-line chemotherapy is longer than 180 days ago may use platinum-based two-drug chemotherapy again. Other patients can only be treated with topotecan monotherapy, the only second-line medicine approved by the FDA. The approval of the second-line treatment of topotecan was based on a phase III study in subjects with recurrent SCLC to compare the efficacy and safety of topotecan monotherapy and the CAV regimen, i.e., cyclophosphamide, adriamycin, and vincristine. The results showed similar efficacy between the two groups in terms of the ORR (24.3% vs. 18.3%, p = 0.285), mPFS (13.3 wks vs. 12.3 wks, p = 0.552), and mOS (25 wks vs. 24.7 wks, p = 0.795). In terms of safety, the incidence of non-hematologic toxicity in the topotecan group was lower than that in the CAV group, mostly Grade 1-2. In terms of hematologic toxicity, there were more Grade > 4 neutropenia cases in the CAV group than in the topotecan group, but the incidences of Grade > 4 thrombocytopenia and Grade 3-4 anemia were higher in the topotecan group ^[18]. Based on 21 meta-analyses published during 1984-2011, the mOS of second-line treatments of SCLC was 6.7 months^[19]. In summary, SCLC has huge unmet clinical needs.

